**Table 1: Visit Windows**

Nominal Visit	Target Study Day	Analysis Visit	Study Day Range
Screening	-30 to -1	Baseline	<=1
Day 1	1		
Week 1	8	Week 1	[2 – 11]
Week 2	15	Week 2	[12 – 22]
Week 4	29	Week 4	[23 – 42]
Week 8	57	Week 8	[43 – 70]
Week 12	85	Week 12	[71 – 98]
Week 16	113	Week 16	[99 – 126]
Week 20	141	Week 20	[127 – 154]
Week 24	169	Week 24	[155 to 182]

For the OLE, the analyses will be based on the nominal study visit as reported on the CRF.

### **3.4. TIMING OF ANALYSES**

#### **3.4.1. Interim Analysis**

When all subjects have completed the blinded treatment period or terminated early from the blinded treatment period and data have been cleaned and forwarded for analysis, the study will be unblinded and the safety and efficacy analysis will be performed according to this SAP. See Section 8.1. for the list of proposed summary table and figures and data listings for the End of Double-Blind Treatment Period analysis.

#### **3.4.2. End of Open Label Analysis**

A final analysis will also be performed at the end of the open-label extension period. See Section 8.2. for the list of proposed summary table and figures and data listings for the End of Open Label Period analysis.

### **4. ANALYSIS POPULATIONS**

The populations for analysis will include the intent-to-treat population (ITT), the safety population (SAF), and the per protocol (PP) population.

#### **4.1. INTENT-TO-TREAT (ITT) POPULATION**

The ITT population is the population of all subjects who are randomized into a treatment group. Subjects in this population will be analyzed according to the treatment group to which they were randomized. The ITT population will be used for all efficacy analyses.

#### **4.2. SAFETY POPULATION**

The Safety population is defined as all randomized subjects who applied at least 1 application of study medication. Subjects in this population will be analyzed according to the treatment which they receive. All safety analyses will be based on this population.

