7. STUDY TREATMENT

7.1. Investigational Study Medication

The study medications for this study are ATI-50002 Topical Solution in dosage strengths of 0.46% and 0.12% and Vehicle Topical Solution. The study medications are formulated as thin clear solutions that are indistinguishable as packaged and labelled. The inactive ingredients include: water, transcutol P, propylene glycol, PEG400, dimethyl sulfoxide (DMSO), kolliphor CS 20, benzyl alcohol, poloxamer 188, and povidone K30.

STUDY MEDICATION INFORMATION				
Study medication name	Double-Blind Period			Open-Label Period
	ATI-50002	ATI-50002	Vehicle	ATI-50002
Dosage Strength	0.46%	0.12%	-	0.46%
Manufacturer	PMRS, Inc., Horsham, PA			
Pharmaceutical Form	Topical Solution			
Container	Amber Glass Bottle, 120 mL with screw cap			
Storage Conditions	59°F to 77°F (15°C to 25°C)			
Dose regimen				
Route	Topical			
Frequency	Twice-daily			
Duration of administration	24 weeks		24 Weeks	
Other supplies	Disposable, single-use droppers will be provided.			

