## **5. STATISTICAL METHODS**

Descriptive statistical methods will also be used to summarize the data from this study, with hypothesis testing performed for the primary and key secondary efficacy endpoints. Unless stated otherwise, the term “descriptive statistics” refers to number of subjects, mean, median, standard deviation, minimum, and maximum for continuous data, and frequencies and percentages for categorical data. For categorical variables, the denominator of percentages will be the number of subjects in the treatment group, except for those collected by study visit and/or scheduled time point, in which case the denominator of percentages will be the number of subjects with a non-missing value at the visit and/or the scheduled time point. If a different denominator is used, this will be identified in the summary table.

All data collected during the study will be included in data listings. Unless otherwise noted, the data will be sorted first by treatment group, subject number, and then by date within each subject number. Assessments indicated as ‘Not Done’ will not be included in the listings.

The term ‘treatment group’ refers to ATI-50002 active groups and matching Vehicle group.

All statistical testing will be two-sided and will be performed using a significance (alpha) level of 0.05 unless otherwise stated. P-values will be presented to three decimal places. For the efficacy endpoints, the ATI-50002 treatment groups will be tested versus vehicle via statistical inference.

The statistical analyses will be conducted with the SAS® software package version 9.4 or higher. All analyses will be subject to formal verification procedures. Specifically, results will be independently verified by a second programmer/statistician or independently hand-checked prior to issuance of the draft statistical report. All documents will be reviewed by the lead statistician to ensure accuracy and consistency.

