#### **5.2.9. Open-Label Extension**

For the open label extension period, efficacy will be evaluated based on the SALT, ALODEX, Scalp-ClinRO, Scalp-PRO, and SGITS. Descriptive summary statistics will be reported for the following:

- SALT score and change from baseline
- ALODEX Score and change from baseline
- Number (%) of subjects for each category of the Scalp-ClinRO (target patch and entire scalp)
- Number (%) of subjects for each category of the Scalp-PRO (target patch and entire scalp)
- Number (%) of subjects for each category of SGITS.

Summaries will include changes from baseline (study day 1) and changes from the end of the DB study (Visit 10). All by visit summaries will utilize the normal study visit based on CRF collection.

The efficacy summaries will be presented for the following subject groups based on the DB treatment assignments and the duration since end of DB period:

- Subjects who were randomized to Vehicle in the double-blind portion of the study
- Subjects who were randomized to ATI-50002 12% in the double-blind portion of the study who also entered the OLE less than 7 days from the end of their DB treatment period
- Subjects who were randomized to ATI-50002 12% in the double-blind portion of the study who also entered the OLE more than 7 days, but less than 60 days from the end of their DB treatment period
- Subjects who were randomized to ATI-50002 12% in the double-blind portion of the study who also entered the OLE at least 60 days from the end of their DB treatment period
- Subjects who were randomized to ATI-50002 46% in the double-blind portion of the study who also entered the OLE less than 7 days from the end of their DB treatment period

- Subjects who were randomized to ATI-50002 46% in the double-blind portion of the study who also entered the OLE more than 7 days, but less than 60 days from the end of their DB treatment period
- Subjects who were randomized to ATI-50002 46% in the double-blind portion of the study who also entered the OLE at least 60 days from the end of their DB treatment period.

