### **5.3. SAFETY**

All safety analyses will be performed on the Safety Population. Values for all safety variables will be listed by subject and visit (as applicable).

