### **5.3.4. Open-Label Extension Safety Analyses**

Adverse events, laboratory values, and vital signs will be used in the OLE period to assess safety. Results occurring in just the OLE period will be reported based on the same treatment groups used for reporting during the DB portion of the study. The same analyses planned for the DB period will be generated for the OLE. Additionally, pooled AE displays will be developed. For the pooled analysis, only AEs in the OLE would apply to the patients randomized to vehicle during the DB

portion of the study. For patients randomized to ATI-502 during the DB portion, their complete AE profile for the entire study should be summarized in the pooled analysis.

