### Section 14.3 Safety

17. Overall Summary of Adverse Events, Safety Population
18. Treatment-Emergent Adverse Events by System Organ Classification, Preferred Term, and Greatest Severity, Safety Population
19. Treatment-Emergent Adverse Events by System Organ Classification and Preferred Term, Safety Population
20. Treatment-Emergent Serious Adverse Events by System Organ Classification and Preferred Term, Safety Population
21. Treatment-Emergent Adverse Events Related to Study Medication by System Organ Classification and Preferred Term, Safety Population
22. Treatment-Emergent Adverse Events Leading to Discontinuation of Study Medication by System Organ Classification and Preferred Term, Safety Population

23. Overall Summary of Adverse Events, Safety Population (Pooled DB and OLE)
24. Treatment-Emergent Adverse Events by System Organ Classification, Preferred Term, and Greatest Severity, Safety Population (Pooled DB and OLE)
25. Treatment-Emergent Adverse Events by System Organ Classification and Preferred Term, Safety Population Safety Population (Pooled DB and OLE)
26. Treatment-Emergent Serious Adverse Events by System Organ Classification and Preferred Term, Safety Population (Pooled DB and OLE)
27. Treatment-Emergent Adverse Events Related to Study Medication by System Organ Classification and Preferred Term, Safety Population (Pooled DB and OLE)
28. Treatment-Emergent Adverse Events Leading to Discontinuation of Study Medication by System Organ Classification and Preferred Term, Safety Population (Pooled DB and OLE)
29. Summary of Hematology Results and Change from Baseline by Visit, Safety Population
30. Summary of Treatment-Emergent Abnormal Hematology by Visit, Safety Population
31. Summary of Serum Chemistry Results and Change from Baseline by Visit, Safety Population
32. Summary of Treatment-Emergent Abnormal Serum Chemistry by Visit, Safety Population
33. Summary of Urinalysis by Visit, Safety Population
34. Summary of Treatment-Emergent Abnormal Urinalysis by Visit, Safety Population
35. Summary of Vital Signs and Change from Baseline, Safety Population

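### Extension-only adverse-event percentages are taken over treated subjects who never entered the extension; in the pooled tables the same fault is confined to vehicle-randomized non-entrants

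*SAP*

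**What the plan says.** **Population.** SAP Section 4 lists three sets: "The populations for analysis will include the intent-to-treat population (ITT), the safety population (SAF), and the per protocol (PP) population". None is tied to the extension. Section 4.2 reads: "The Safety population is defined as all randomized subjects who applied at least 1 application of study medication". Protocol Section 7.1 counts vehicle as study medication: "The study medications for this study are ATI-50002 Topical Solution in dosage strengths of 0.46% and 0.12% and Vehicle Topical Solution". A vehicle subject who never received ATI-50002 is therefore a member. SAP Section 5.3 makes no exception for the extension: "All safety analyses will be performed on the Safety Population". In Section 8.2, the extension-only AE tables (items 17-22) and the pooled AE tables (items 23-28) all carry the Safety population label; the first pooled title begins "Overall Summary of Adverse Events, Safety Population (Pooled DB and OLE".

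**Denominator.** For categorical variables not collected by visit, SAP Section 5 says that "the denominator of percentages will be the number of subjects in the treatment group". Variables collected by visit use the subjects with a value at that visit. Section 5.3.4 fixes the columns, in a sentence cut here before its last word: "Results occurring in just the OLE period will be reported based on the same treatment groups used for reporting during the DB portion of the".

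**Numerator.** Under SAP Section 3.3.6, an extension AE is treatment-emergent only from the start of open-label medication. For the pooled displays, Section 5.3.4 counts only extension events for vehicle-randomized subjects, and events from the whole study for active-randomized subjects.

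**Entry.** A subject may decline the extension (Protocol 5.5), must meet further criteria (Protocol 5.5.1), and must have completed Visit 10 or 11 (SAP 1.1).

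**The concern.** An AE percentage is meant to estimate risk among people exposed to the drug in the period tabulated. A subject who declined, was ineligible or left during the double-blind period has no first open-label dose, so cannot have a treatment-emergent extension event. Kept in the denominator, that subject is read as exposed and event-free. The direction is certain as soon as one treated subject does not enter: the printed rate is too low.

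The long-term objective includes the safety and tolerability of the 0.46% strength, and these tables address that part directly. If entry differs by randomized arm, the columns are deflated by different amounts, so an apparent contrast between arms could reflect uptake alone.

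**Working it through.** The plan states no extension entry rate and no extension AE rate, so it has no figure of its own to reproduce here. The entry fraction is varied as an assumption.

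**Inputs**
- 40 subjects per arm, 120 in all (SAP 3.1), assuming every one was treated and so belongs to the Safety population.
- f = subjects applying open-label drug / Safety population; assumed 50%, 70%, 90%.
- p = proportion of OLE-treated subjects with an extension AE; 20% for illustration.

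**Extension-only AE tables (items 17-22).** In a column with S Safety subjects, f × S enter and p × f × S have an event. The SAP divides by S:

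printed rate = (p × f × S) / S = f × p

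The relative understatement is 1 − f. When no event is seen, the one-sided 95% upper bound is 1 − 0.05^(1/n). With n = 40 it is 7.2%; the last column uses entrants only.

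| Assumed f | Entrants of 40 | Printed rate, true 20% | Zero-event upper bound, entrants |
|---|---|---|---|
| 50% | 20 | 0.5 × 20% = 10% | 13.9% |
| 70% | 28 | 0.7 × 20% = 14% | 10.1% |
| 90% | 36 | 0.9 × 20% = 18% | 8.0% |

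In the other direction, 8 subjects with an event print as 8/40 = 20.0%. Among entrants that is 8/36 = 22.2%, 8/28 = 28.6% or 8/20 = 40.0%.

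If one arm had 50% entry and another 90%, the same true 20% would print as 10% and 18%.

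**Pooled AE tables (items 23-28).** Active-randomized subjects received ATI-50002 in the double-blind period and their events there count, so they belong in the denominator whether or not they entered. Vehicle-randomized subjects contribute extension events only, so only those who entered belong. The SAP does not state the column layout. Assuming one all-active column:

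- denominator as written: 120
- correct denominator: 80 + 40f = 100, 108 or 116
- printed / correct: 100/120 = 0.833, 108/120 = 0.900, 116/120 = 0.967

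The understatement is then 17%, 10% or 3%. If the columns were instead by randomized arm, the active columns would be right and the vehicle column would carry the full factor f.

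**By-visit tables (items 29-35 and SAP 5.2.9).** Items 29-34 are titled by visit, and SAP 5.3.2 has vital signs (item 35) summarized by visit. The 5.2.9 summaries are also by visit. The denominator is subjects with a value at the visit. A non-entrant has no extension value and drops out, so beyond the header N there is little to dilute.

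**The case against.** The best defence is that the SAP leaves room to do this correctly. Section 5 allows a different denominator if the table identifies it. Section 7 says that the header N need not equal the number summarized and that each module should show how many subjects contribute. A programmer might well restrict to entrants. This stands as permission only: no such denominator is specified for any extension AE table, and the table list names the Safety population. Section 7 speaks of missing values, whereas a subject with no AE record is normally read as having no event, not as missing. The study is also unblinded after the double-blind period (SAP 3.4.1), so a denominator left open would be settled with treatment known.

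Section 4.2 also says subjects are analyzed by the treatment they receive. That governs the column a subject falls in, not membership of the population, and Section 5.3.4 keeps the double-blind columns.

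On consequence, much of the defence holds. The extension has no concurrent control, the tables print counts beside percentages, and disposition and listings are planned, so a careful reader could probably rebuild the right rate.

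Three stronger readings are tempting and are not supported:
- *Every extension safety table is diluted.* The by-visit rule protects items 29-35.
- *The pooled rates shrink by the entry fraction.* They do not, because active-randomized subjects are rightly counted.
- *Extension efficacy has the same fault, because the vehicle group in SAP 5.2.9 is given as "Subjects who were randomized to Vehicle in the double-blind portion of the study" with no entry condition, while the active groups have one.* Those summaries are by visit, so non-entrants supply no extension values. The omission would matter beyond the header N and any baseline or Visit 10 rows only if last-observation imputation ran on into the extension, which 5.2.9 does not say.

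**Conclusion.** The point holds for the AE tables. Followed literally, items 17-22 understate AE incidence among OLE-treated subjects by a relative 1 − f: 50%, 30% or 10% at assumed entry of 50%, 70% or 90%. Items 23-28 are wrong only through vehicle-randomized non-entrants. On the stated assumptions of one all-active column and 40 treated per arm, their rates are about 83% to 97% of the correct value. The direction is certain unless every treated subject enters; the size cannot be known from the documents.

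This should be corrected before the extension tables are produced. It does not touch the double-blind analyses, and no hypothesis test rests on it.

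A separate and minor matter: for each active arm, the groups in SAP 5.2.9 cover gaps of under 7 days, over 7 but under 60 days, and 60 days or more. A subject entering at exactly 7 days belongs to none. This has no bearing on the safety denominators.

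**What to change.** 1. In SAP Section 4, define an OLE Safety population: subjects who applied open-label medication at least once. Name it as the denominator for Section 8.2 items 17-22.
2. For items 23-28, use subjects who applied ATI-50002 at least once in either period, so that vehicle-randomized subjects count only if they were treated in the extension. State the column layout.
3. Carve these tables out of the all-safety-analyses statements in Sections 4.2 and 5.3. Items 29-35 need no change beyond a header N that reflects extension entrants.
4. In Section 5.2.9, make the gap categories contiguous so that day 7 is assigned.

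The cost is a few sentences and population flags, with no new data. The downside is smaller denominators and higher printed AE percentages.

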#### **4.3. PER PROTOCOL (PP) POPULATION**

The Per-Protocol (PP) population is defined as all subjects who are randomized and do not have any major protocol violations. Major protocol violations that will lead to exclusion from the PP are defined as:

1. Inclusion or Exclusion criteria not met
2. Concomitant medications taken during the study that interfere with efficacy
3. Did not apply at least 75% of study medication

4. Did not complete Week 24 (Visit 10).

This population will be used for supportive analyses of key efficacy analyses.

## **5. STATISTICAL METHODS**

Descriptive statistical methods will also be used to summarize the data from this study, with hypothesis testing performed for the primary and key secondary efficacy endpoints. Unless stated otherwise, the term “descriptive statistics” refers to number of subjects, mean, median, standard deviation, minimum, and maximum for continuous data, and frequencies and percentages for categorical data. For categorical variables, the denominator of percentages will be the number of subjects in the treatment group, except for those collected by study visit and/or scheduled time point, in which case the denominator of percentages will be the number of subjects with a non-missing value at the visit and/or the scheduled time point. If a different denominator is used, this will be identified in the summary table.

All data collected during the study will be included in data listings. Unless otherwise noted, the data will be sorted first by treatment group, subject number, and then by date within each subject number. Assessments indicated as ‘Not Done’ will not be included in the listings.

The term ‘treatment group’ refers to ATI-50002 active groups and matching Vehicle group.

All statistical testing will be two-sided and will be performed using a significance (alpha) level of 0.05 unless otherwise stated. P-values will be presented to three decimal places. For the efficacy endpoints, the ATI-50002 treatment groups will be tested versus vehicle via statistical inference.

The statistical analyses will be conducted with the SAS® software package version 9.4 or higher. All analyses will be subject to formal verification procedures. Specifically, results will be independently verified by a second programmer/statistician or independently hand-checked prior to issuance of the draft statistical report. All documents will be reviewed by the lead statistician to ensure accuracy and consistency.

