#### **3.3.4. Missing Data and Outliers**

For missing clinical assessments, the method of last observation carried forward (LOCF) will be used to impute values. The last non-missing value prior to the missing assessment will replace the missing values. For subjects who terminate early, missing assessment after the date of early termination will be replaced by the LOCF method.

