### **5.2.5. Secondary Efficacy Analysis**

Descriptive statistics will be presented for all secondary efficacy endpoints.

The mean percent change from baseline in the ALODEX score (percent regrowth); the mean change from baseline in SALT and the mean change from baseline in ALODEX will be analyzed using the methods planned for the primary efficacy analysis. The calculated DLQI total score ranges from 0 to 30. This mean change from baseline in DLQI will also utilize the MMRM analysis as planned for the primary efficacy analysis.

Responder-type analyses are planned based on the SALT, ALODEX, Scalp-ClinRO, and Scalp-PRO. The responder definitions include:

- The proportion of subjects achieving a  $\geq 50\%$  hair regrowth compared with baseline for SALT and for ALODEX scores
- Proportion of subjects achieving an absolute SALT score  $\leq 10$
- Proportion of subjects with  $\geq 2$ -point improvement in Scalp-ClinRO for the Target Area
- Proportion of subjects with  $\geq 2$ -point improvement in Scalp-PRO for the Target Area
- Proportion of subjects with  $\geq 1$ -point improvement in Scalp-ClinRO for the entire scalp
- Proportion of subjects with  $\geq 1$ -point improvement in Scalp-PRO for the entire scalp

The observed proportion of responders and associated 95% CI will be presented. Adjusted rates and 95% CI will be obtained from a logistic regression model with factors for treatment and baseline SALT score group. The p-value for the overall global test that  $\beta = 0$  for each factor will be presented. The adjusted odds ratios (95% CI) for being a responder (active/vehicle) will be presented along with the associated p-value.

The questionnaires Scalp-PRO, Scalp-ClinRO, PhGIS, and SGIS are collected on a 1-5 scale. The frequency of responses for each value will be reported by visit and treatment group. Additionally, change status will be categorized as “Better by x points” when the score decreases from baseline by x points, and as “Worse by x points” when the score increases by x points. For these scales, a stratified Wilcoxon rank sum test will be used at each visit to obtain a p-value to compare the change status of each active treatment group to the vehicle.

For SGITS, PhGIC, and SGIC, the frequency of responses will be summarized for each scheduled collection timepoint. A stratified Wilcoxon rank sum test will be used at each visit to obtain a p-value to compare the results of each active treatment group to the vehicle.

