## 7. PROGRAMMING CONVENTIONS

- Page orientation, margins, and fonts: Summary tables, listings, and figures will appear in landscape orientation. There should be a minimum of a 1” boundary on the upper (bound) edge, and a minimum of a 1.0” boundary on the remaining three edges. Output should be printed in Courier New with a point size of 8. Titles may be printed using a larger font (e.g., Arial point size 10).
  - Identification of analysis population: Every summary table and figure should clearly specify the analysis population being summarized. Listings will be prepared for all subjects.
  - Group headers: In the summary tables, the group headers will identify the summary group and the sample size for the indicated analysis population. Of note, the header’s sample size does not necessarily equal the number of subjects summarized within any given summary module; some subjects in the analysis population may have missing values and thus may not be summarized.
  - Suppression of percentages corresponding to null categories: When count data are presented as category frequencies and corresponding percentages, the percent should be suppressed when the count is zero in order to draw attention to the non-zero counts.
  - Presentation of sample sizes: Summary modules should indicate, in one way or another, the number of subjects contributing to the summary statistics presented in any given summary module. As mentioned above, this may be less than the number of subjects in the analysis population due to missing data.
    - In the quantitative modules describing continuous variables (and thus presenting sample size, means, and standard deviations), the sample size should be the number of non-missing observations.
    - For categorical variables that are presented in frequency tables, the module should present the total count in addition to the count in each category. Percentages should be calculated using this total as the denominator, and the percentage corresponding to the sum itself (that is, 100%) should be presented to indicate clearly to a reviewer the method of calculation.
  - Sorting: Listings will be sorted by treatment group, subject number and date, if applicable.

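### The SAP does not settle how early withdrawals count in the seven secondary responder endpoints, and neither rule it offers treats leaving before Week 24 as non-response

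*SAP*

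**What the plan says.** SAP 5.2.5 introduces the outcomes: "Responder-type analyses are planned based on the SALT, ALODEX, Scalp-ClinRO, and Scalp-PRO". There are seven: at least 50% regrowth on SALT, the same on ALODEX, SALT of 10 or less, and improvement on Scalp-ClinRO and Scalp-PRO, each for the target area and for the entire scalp. On analysis it says "The observed proportion of responders and associated 95% CI will be presented" and "Adjusted rates and 95% CI will be obtained from a logistic regression model with factors for treatment and baseline SALT score group". It gives no rule for a missing response.

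Three general provisions could supply one:

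- SAP 3.3.4 (LOCF): "The last non-missing value prior to the missing assessment will replace the missing values", and "For subjects who terminate early, missing assessment after the date of early termination will be replaced by the LOCF method".
- SAP 5 (by-visit categorical data): "the denominator of percentages will be the number of subjects with a non-missing value at the visit". A table may use another denominator if it identifies it.
- SAP 7 (header counts): "some subjects in the analysis population may have missing values and thus may not be summarized".

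SAP 4.1 sets the population: "The ITT population will be used for all efficacy analyses". In SAP 8.1 the SALT analysis tables are marked LOCF or Observed. Responder Tables 14.2.3.1 to 14.2.3.7 carry neither mark. The observed-data repeat in SAP 5.2.3 covers the primary endpoint only.

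**The concern.** The question is response at Week 24 among all subjects randomised. LOCF answers a different one, namely status when last seen. A subject who had regrown hair at Week 8 and then left is a Week 24 responder. Protocol 2.1 describes patchy disease as fluctuating, with spontaneous regrowth common, so an early regrowth is a weak stand-in for Week 24. The carry is longest for the four Scalp-ClinRO and Scalp-PRO outcomes, which are scheduled after baseline only at Weeks 4, 12 and 24. Unless exit assessments were obtained, the carried value is from Week 12 or earlier, a gap of at least 12 weeks. A non-missing denominator would instead describe those who stayed.

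Withdrawal may be related to outcome or treatment: Protocol 5.9 lists adverse events and prohibited therapy among the reasons. At stake are the responder differences, odds ratios and p-values. Because SAP 5 allows a table to identify its own denominator, the text also leaves room to settle the choice after the unblinding described in SAP 3.4.1.

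**Working it through.** **The plan's own figure.** The only power statement (SAP 3.1) is 80% for 24 points, SD 38, 40 per group, two-sided 0.05. The standardised difference is 24 / (38 × √(2/40)) = 24 / 8.497 = 2.82, which gives 80.6% by the normal formula and 79.7% by the noncentral t with 78 df. It reproduces, but it concerns the continuous primary endpoint. Neither document gives a dropout rate, a response rate or a power figure for any responder endpoint.

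**A subject who leaves at Day 60.** Protocol 5.9 asks for the Visit 10 assessments at exit. SAP 3.3.7 assigns assessments by study day, so they fall in the Week 8 window (Days 43 to 70) and Week 24 (Days 155 to 182) stays empty. SAP 3.3.4 then fills Week 24 with the last value. If 3.3.4 is taken not to reach the responder tables, SAP 5 drops the subject. For a subject with only a baseline value, 3.3.4 does not say whether baseline may be carried. Neither route makes the withdrawal itself a non-response.

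**Size.** For each arm let c be response among completers, d the dropout proportion, and f the share of dropouts last seen as responders.

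- Non-missing denominator: c
- LOCF: c(1 − d) + f·d
- Withdrawal as non-response, all randomised: c(1 − d)

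With subscripts a (active) and v (vehicle), the gap in the difference relative to the third rule is f_a·d_a − f_v·d_v for LOCF and c_a·d_a − c_v·d_v for the non-missing denominator.

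All inputs are assumptions: c = 40% active and 20% vehicle; f = 20% active and 10% vehicle. Entries are the difference in points, with the crude odds ratio in brackets.

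| Dropout active / vehicle | Non-missing | LOCF | Non-response |
|---|---|---|---|
| 0% / 0% | 20 (2.67) | 20 (2.67) | 20 (2.67) |
| 15% / 15% | 20 (2.67) | 18.5 (2.59) | 17 (2.52) |
| 30% / 30% | 20 (2.67) | 17 (2.52) | 14 (2.39) |
| 10% / 30% | 20 (2.67) | 21 (2.99) | 22 (3.46) |
| 30% / 10% | 20 (2.67) | 15 (2.20) | 10 (1.77) |

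The last row in full:

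- LOCF: active 0.40 × 0.70 + 0.20 × 0.30 = 34%; vehicle 0.20 × 0.90 + 0.10 × 0.10 = 19%; difference 15; odds ratio (0.34 × 0.81) / (0.66 × 0.19) = 2.20.
- Non-response: 28% against 18%; difference 10; odds ratio (0.28 × 0.82) / (0.72 × 0.18) = 1.77.

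If f = 0 in both arms, LOCF equals the non-response rule (15% dropout in both arms: 20 / 17 / 17).

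**No effect in completers** (c = 20%, f = 10% in both arms). Equal 15% dropout gives 0 under all three rules. Dropout of 10% active and 30% vehicle gives 0 (non-missing), +2 (LOCF) and +4 (non-response). Reversing the dropout gives 0, −2 and −4.

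**The case against.** The strongest reply is that the SAP does have a rule. Section 3.3.4 fills gaps first and names early terminators, so the SAP 5 denominator touches only what is still missing, and it governs descriptive percentages rather than the logistic models. In 5.2.5 the word observed contrasts with the adjusted rates that follow and need not mean observed-case. Missing table labels are weak evidence: DLQI Table 14.2.9.2 is unlabelled too, although 5.2.5 assigns it the primary method. All of this stands, and it makes LOCF the more natural reading. A reader might infer that the responder tables and models are completer analyses; the text does not establish that, and the larger gaps in the table rest on that weaker reading.

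Second, a non-response rule is not a neutral benchmark. With no effect in completers and dropout of 10% against 30%, it produces a 4-point difference by itself. Under LOCF the gap cancels when f·d is equal in the two arms, and a dropout last seen as a non-responder is already counted as one. This also stands. The rule is a composite endpoint, to be chosen because it answers the Week 24 question in all randomised subjects.

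Third, these are secondary Phase 2 endpoints, and SAP 5.1 reports early termination and its reasons by arm. That limits the consequence. It does not supply the missing rule, and disposition tables do not show which withdrawn subjects were carried as responders.

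**Conclusion.** The point holds as a gap in specification with a possible, not demonstrated, distortion. SAP 5.2.5 leaves the rule unstated. LOCF, the likelier one, credits early leavers with their last status. No analysis, main or sensitivity, counts withdrawal before Week 24 as non-response.

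A reader might go further and conclude that the responder differences are biased. The documents do not support that: without dropout rates, last-seen status or a stated estimand, neither presence, sign nor size can be derived. Under the assumed inputs the LOCF gap runs from −1 to +5 points and the non-missing gap from −2 to +10. Both are zero without dropout, and the LOCF gap is zero if no dropout was last seen as a responder.

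A reader might also infer that responder definitions for pivotal trials are at risk. That work belongs to a secondary objective that SAP 2 places outside its scope. The primary MMRM is unaffected. The change should be made, but it is not critical to the trial's main conclusion.

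**What to change.** Before unblinding:

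- In SAP 5.2.5 and 5.2.7, state that for the Week 24 responder tables and logistic models an ITT subject who discontinued before Week 24 and has no observed assessment in the Week 24 window is a non-responder. The denominator is all subjects randomised to the arm.
- State separately the rule for a completer with an isolated missing value, and the rule for the earlier visits plotted under 5.2.8.
- Exempt these endpoints from the LOCF rule in 3.3.4 and the denominator rule in 5 for the main analysis, and keep LOCF as a labelled sensitivity analysis.
- Label Tables 14.2.3.1 to 14.2.3.7 and the subgroup responder tables (14.2.13.1 to 14.2.18.2) accordingly.

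The cost is SAP wording and one derivation flag, with no new data. The downside is lower reported response in arms with dropout, and a composite endpoint that also reflects differential withdrawal. The LOCF sensitivity analysis makes that visible.
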